#### Risk Factors

- Documented history of coronary artery disease
- Heart failure (New York Heart Association Class 3 or 4)
- Documented history of stroke
- Chronic lung disease (eg, asthma or chronic obstructive pulmonary disease) requiring treatment
- Diabetes mellitus, requiring at least 1 prescription medicine for management
- Documented CKD with an estimated glomerular filtration rate  $<30$  mL/min, not on dialysis
- Obesity (Class 2 or 3; body mass index  $>34.9$  kg/m^2)
- On immunosuppressive therapy
- Oxygen saturation between 90 and 95% with or without supplemental oxygen

4. Admitted to a hospital (or controlled facility such as an emergency room, urgent care facility, temporary/modular hospital, infusion center, clinical research unit, etc; hereafter referred to as hospital) for observation and/or treatment
5. If female, must be postmenopausal, surgically sterile, or if of childbearing potential, must be practicing 2 effective methods of birth control during the study and through 30 days after completion of the study.
6. For females of childbearing potential, a urine pregnancy test must be negative at the Screening Visit.
7. If male, must be surgically sterile or willing to practice 2 effective methods of birth control during the study and through 30 days after completion of the study.
8. Must be willing and able to give informed consent and comply with all study procedures.

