#### **9.3.1 Stopping Rules**

For the second, third, and fourth interim analysis, the primary endpoint will be assessed for futility by the DSMB. Enrollment will be stopped if the conditional power is  $<10\%$  based on the percentage of subjects classified in categories 4 through 8 on the 8-point WHO Ordinal Clinical Scale for RBT-9 versus placebo.

Efficacy will be declared at the fourth interim analysis if the conditional power is  $>80\%$  (with all subjects followed through Day 28). If efficacy is declared, the DSMB will advise regarding study continuation.

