#### **11.1 Endpoints**

The following efficacy endpoints are defined for the study.

Primary Endpoint: Percentage of subjects in each treatment group in categories 4 through 8 of the 8-point WHO Ordinal Clinical Scale through Day 28.

Secondary Endpoints:

- Time to first occurrence of either death from any cause or new/worsened organ dysfunction through Day 28, defined as at least one of the following:
  - Respiratory decompensation
  - New or worsening congestive heart failure
  - Requirement of vasopressor therapy and/or inotropic or mechanical circulatory support
  - Ventricular tachycardia or fibrillation lasting at least 30 seconds and/or associated with hemodynamic instability or pulseless electrical activity, or resuscitated cardiac arrest

- Initiation of renal replacement therapy.
- Percentage of subjects who are alive at Day 28.
- Among subjects who begin oxygen therapy, mean change from initiation to last day on oxygen or Day 28 (whichever happens first) in SpO2/FiO2 ratio.
- Percentage of subjects with fever through Day 28.
- Percentage of subjects who develop AKI, as determined by the Investigator, through Day 28.
- Percentage of subjects with new or worsening congestive HF through Day 28.
- Percentage of subjects with ventricular tachycardia or fibrillation lasting at least 30 seconds and/or associated with hemodynamic instability or pulseless electrical activity, or resuscitated cardiac arrest through Day 28.
- Percentage of subjects who remain hospitalized at Day 28.
- Length of hospitalization through Day 28.
- Number of oxygen-free days through Day 28.
- Percentage of subjects transferred to the ICU through Day 28.
- Number of days on mechanical ventilation through Day 28.
- Time to and duration of vasopressor or inotrope utilization through Day 28.
- Percentage of subjects who begin dialysis through Day 28.

Exploratory Endpoints:

- Duration of COVID-19 symptoms through Day 56

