#### **11.6 Sample Size Calculations**

The following table summarizes the RBT-9 advantages (15-18%) that can be detected with 84-85% power and 252 subjects for a 2-sided hypothesis test with 5% overall Type 1 error with 2-sided 4.5% Type 1 error remaining at the final analysis; this alpha spend accounts for the preplanned interim analyses.

Two group  $\chi^2$  test: Null hypothesis is Equal Failure %s (odds ratio = 1)

	84-85% Power			Two-sided p=0.045		
	1	2	3	1	2	3
Test significance level, $\alpha$	0.045	0.045	0.045	0.045	0.045	0.045
1 or 2-sided test?	2	2	2	2	2	2
Placebo Failure %, $\pi_1$	25%	32%	38%	25%	32%	38%
RBT Failure %, $\pi_2$	10%	15%	20%	14.6%	20.4%	25.7%
Odds ratio, $\pi_2(1-\pi_1)/[\pi_1(1-\pi_2)]$	0.333	0.375	0.408	0.513	0.545	0.564
Power (%)	84	85	84	NA	NA	NA
Placebo sample size, n1	84	84	84	84	84	84
RBT sample size, n2	168	168	168	168	168	168
Ratio: n2 / n1	2	2	2	2	2	2
N = n1 + n2	252	252	252	252	252	252

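### Several secondary day counts and the Day 28 hospital-status endpoint score an early death as a good result, and the SpO2/FiO2 endpoint compares a subset formed after randomization

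*Combined protocol and SAP*

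**What the plan says.** Section 11.1, repeated in the synopsis (Section 4, Statistics), includes among the secondary endpoints "Length of hospitalization through Day 28", "Number of days on mechanical ventilation through Day 28", "Percentage of subjects who remain hospitalized at Day 28", "Number of oxygen-free days through Day 28", and the time to and duration of vasopressor or inotrope use. None of these entries says what value a subject who dies receives.

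The analysis text does not supply one. Sections 11.3 and 11.4 give a repeated-measures model for continuous endpoints and Kaplan-Meier, log-rank and Cox methods for time-to-event outcomes, and Section 11.3 rules out imputation. Section 12 provides for censoring at withdrawal but does not mention death. Section 11 leaves data handling to a separate SAP, which is not part of the document reviewed.

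The SpO2/FiO2 endpoint is worded "Among subjects who begin oxygen therapy, mean change from initiation to last day on oxygen" or Day 28, whichever comes first. One qualifying risk factor in Section 9.1 is "Oxygen saturation between 90 and 95% with or without supplemental oxygen", so some subjects may already be on oxygen at entry. The text does not say whether they count as having begun it.

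**The concern.** A subject who dies on Day 4 has had a four-day stay, at most four ventilator or vasopressor days, and is not in hospital on Day 28. On these endpoints that record looks better than the record of a subject who survives a long illness. A drug that keeps severely ill patients alive adds long-stay survivors to its own arm, and a drug that hastens death removes them. In either case the endpoint can run opposite to mortality. For oxygen-free days the text is ambiguous, because it does not say whether days after death count as free.

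The SpO2/FiO2 issue is different in kind. Starting oxygen happens after randomization, and category 4 of the primary endpoint is hospitalized on oxygen, so the trial itself is testing whether RBT-9 changes who needs it. Those who start oxygen in the two arms need not be comparable.

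What is at stake is how these secondary results read.

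**Working it through.** **The plan's own figures.** Section 11.6 says: "The following table summarizes the RBT-9 advantages (15-18%) that can be detected with 84-85% power and 252 subjects". With 84 placebo and 168 RBT-9 subjects and two-sided alpha 0.045, the pooled chi-square calculation gives 84.9%, 85.6% and 84.6%, against the stated 84, 85 and 84. The table reproduces. The plan gives no figure for the secondary endpoints. Taking the table's failure rate as the category 4-8 rate, the planned ratios of RBT-9 to placebo are r = 10/25 = 0.40, 15/32 = 0.47 and 20/38 = 0.53.

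**Assumed inputs.** The documents give no mortality, timing or duration figures. I assume mortality m of 5% on RBT-9 and 10% on placebo. Results below are RBT-9 vs placebo.

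1. *Length of stay.* Mean = (1 − m) × survivor stay + m × day of death. With survivors staying 10 days in both arms and deaths on Day 4:
   - 0.95×10 + 0.05×4 = 9.7 vs 0.90×10 + 0.10×4 = 9.4, which is 0.3 days against RBT-9.
   - In general the shift is mortality gap × (survivor stay − day of death). It is 0.12 for a 2-point gap and 0.48 for 8 points; with the 5-point gap it is 0.05 if survivors stay 5 days and 0.5 if they stay 14.
   - Standard error = SD × √(1/168 + 1/84) = 0.1336 × SD. For an assumed SD of 5 to 10 days this is 0.67 to 1.34, so 0.3 days is 0.45 to 0.22 standard errors.
   - The reversal disappears if deaths fall on Day 10 or later, or if RBT-9 survivors leave 0.32 days sooner (0.95x + 0.2 = 9.4 gives x = 9.68).
   - Hospital-free days with death scored 0: 0.95×18 = 17.1 vs 0.90×18 = 16.2, in line with mortality.

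2. *Ventilator days.* Assume 15% ventilated on placebo and 15% × r on RBT-9, with all deaths among the ventilated after 3 ventilator days and ventilated survivors having 12 days. Placebo: 0.05×12 + 0.10×3 = 0.90. RBT-9: (0.15r − 0.05)×12 + 0.05×3.
   - Equal shares (r = 1): 1.35 vs 0.90, against RBT-9.
   - Plan ratios: 0.27, 0.39 and 0.50 vs 0.90, no reversal.
   - Break-even r is 0.75 (0.79 if ventilated survivors have 8 days, 0.92 if 4).

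3. *Remain hospitalized at Day 28.* Assume 5% on placebo, as a share of all randomized. Let f be the share of the 5 points of averted deaths still inpatient at Day 28. RBT-9 = 5r + 5f.
   - Other inpatients unchanged (r = 1): 6% to 10% vs 5% for f = 0.2 to 1.
   - Plan ratios: RBT-9 exceeds 5% only if f > 1 − r, that is 0.60, 0.53 or 0.47. At f = 1 it reads 7.0%, 7.3% or 7.6%.
   - Dead or hospitalized at f = 1 is 5 + 5r + 5f = 12.0%, 12.3% or 12.6% vs 10 + 5 = 15%, in line with mortality.

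4. *Oxygen-free days.* Use oxygen only in the planned category 4-8 share c, 10 oxygen days per surviving user, Day 4 deaths on oxygen throughout, and days after death counted as free. Mean = 28 − [(c − m)×10 + m×4].

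| Planned c, placebo / RBT-9 | RBT-9 | Placebo |
|---|---|---|
| 25% / 10% | 28 − (0.5 + 0.2) = 27.3 | 28 − (1.5 + 0.4) = 26.1 |
| 32% / 15% | 28 − (1.0 + 0.2) = 26.8 | 28 − (2.2 + 0.4) = 25.4 |
| 38% / 20% | 28 − (1.5 + 0.2) = 26.3 | 28 − (2.8 + 0.4) = 24.8 |

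   There is no reversal in any scenario, even under the convention least favourable to RBT-9.

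5. *Vasopressor or inotrope duration* has the same gap as ventilator days; no separate figure was computed. *SpO2/FiO2*: no size or direction of bias is claimed.

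**The case against.** The strongest reply is that scoring deaths is data handling, which Section 11 assigns to a SAP not seen here. A reader might infer that the trial has no death rule at all. The documents do not support that: they show only that the protocol text is silent.

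The second reply is that the reversals need chosen inputs: early deaths, and a drug that halves mortality but barely changes ventilation, oxygen use or discharge. This largely stands. A tempting stronger reading is that oxygen-free days change direction according to how days after death are counted. That does happen if every survivor spends 10 days on oxygen: 0.95×18 + 0.05×24 = 18.3 vs 0.90×18 + 0.10×24 = 18.6 if those days count as free, and 17.1 vs 16.2 if they do not. But Section 11.6 puts only 25-38% of placebo subjects in categories 4-8, and at the planned rates the reversal is gone. A relative fall of about 8-12% in the category 4-8 share is enough to remove it, while the plan assumes 47-60%.

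Third, these are items in a long secondary list, and Day 28 survival is reported beside them, so a mortality difference would be visible. This also stands, and it sets the weight of the point. It does not remove the point: the endpoint definitions as written still reward early death.

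Fourth, scoring death as 0 is one convention among several, and the SpO2/FiO2 restriction is openly stated. Both are fair. The first leaves the choice of rule open but not the need for one, and the second makes this a matter of labelling.

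**Conclusion.** The point holds as a low-severity one. In the supplied text, length of stay, ventilator days, vasopressor or inotrope duration and Day 28 hospital status treat an early death as favourable, and under some inputs the first, second and fourth were shown to run opposite to mortality. The mortality, timing and duration inputs are assumptions. The stay shift is a fraction of a standard error, ventilator days do not reverse at the plan's ratios, and hospital status reverses there only if more than 47-60% of averted deaths are still inpatients at Day 28.

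A reader might infer that the trial could declare success, or stop, on misleading grounds. The documents do not support that. Death is category 8 of the scale behind the primary endpoint and the Wilcoxon test, it is part of the organ-dysfunction composite, and survival is its own endpoint. Section 9.3.1 states: "For the second, third, and fourth interim analysis, the primary endpoint will be assessed for futility by the DSMB". The day counts have no role in that rule.

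The SpO2/FiO2 endpoint is not a randomized comparison. It would go beyond the documents to say which arm it favours.

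**What to change.** In Section 11.1 and the synopsis:

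- Define the day counts as days alive and free of hospital, ventilator, oxygen and vasopressor or inotrope through Day 28, with death by Day 28 scored 0. Keep the raw durations as descriptive summaries.
- Report dead or hospitalized at Day 28 in place of, or beside, hospitalized alone.
- Label the SpO2/FiO2 comparison descriptive, and state whether subjects on oxygen at entry are included.

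State these rules in the protocol, or confirm them in the SAP, before by-arm efficacy data are reviewed. Timing matters because assignment is open-label (Sections 9.6 and 10.5) and interim looks at the primary endpoint by arm are planned (Section 11.7).

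Optional: a rank test for the day counts stratified by time since diagnosis and, if time to discharge or extubation is analysed, death treated as a competing event.

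The cost is wording only. The counts use hospital, ventilator, oxygen, vasopressor or inotrope and death dates that the existing endpoints already need. The downside is that composite counts are slightly less direct to describe, and the score of 0 for death is a convention that should be stated as such.

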## 11.2 Study Populations

The primary efficacy analysis will be conducted in the Intent-to-Treat population (all randomized subjects), and a secondary efficacy analysis will be conducted in the Per Protocol population (all randomized subjects who had no major protocol deviations). Safety analyses will be conducted in all subjects receiving any study drug.

## 11.3 Data Analysis

The primary efficacy endpoint will be mapped to a binary endpoint (% categories 4-8) and then will be analyzed using a two-sided Fisher Exact test and using a logistic regression model to control for the stratification factors; the method of Firth will be used to predict outcomes. A two-sided Wilcoxon rank sum test will be used to compare the primary efficacy endpoint distributions for the two treatment groups. Continuous endpoints will be evaluated using a mixed model repeated measures (MMRM) analysis using a compound symmetry (CS) error structure. Time to event outcomes (eg, extubation, WHO progression, death) will be displayed using a Kaplan-Meier (KM) lifetable and treatment distributions compared using a stratified log-rank test and Cox proportional hazards model to control for time since COVID-19 diagnosis.

When appropriate, summary statistics will be provided (number of non-missing values, mean, median, standard deviation, minimum, and maximum for continuous variables and number and percentage of patients for categorical variables) by treatment group for all measures, including demographic and baseline assessments, safety, and efficacy endpoints. Baseline for all safety and efficacy endpoints is defined as the last observations before administration of study drug. No imputation will be used for missing data.

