**Statistics continued:**

**Efficacy Analysis:** The primary efficacy endpoint will be analyzed using a 2-sided Fisher Exact test and a logistic regression model to control for the stratification factor (time since COVID-19 diagnosis); the method of Firth will be used to predict outcomes. A 2-sided Wilcoxon rank sum test will be used to compare the distributions of scores on the 8-point WHO Ordinal Clinical Scale for the 2 treatment groups. Continuous endpoints will be evaluated using a mixed model repeated measures analysis using a compound symmetry error structure. Time to event outcomes (e.g., extubation, hospital discharge, death) will be displayed using a Kaplan-Meier life table and treatment distributions compared using a stratified log-rank test and Cox proportional hazards model to control for time since diagnosis and treatment including the interaction term. A Greenwood test will be performed using the Day 28 estimates from the Kaplan-Meier lifetable.

**Safety Analysis:** Safety measures including adverse events, clinical laboratory tests, vital signs, physical examinations, and concomitant medication usage will be summarized descriptively by treatment group.

When appropriate, summary statistics will be provided (number of non-missing values, mean, median, standard deviation, minimum, and maximum for continuous variables and number and percentage of patients for categorical variables) by treatment group for all measures, including demographic and baseline assessments, safety, and efficacy endpoints. Baseline for all safety and efficacy endpoints is defined as the last observations before administration of study drug. No imputation will be used for missing data.

**Interim Analyses:** A group sequential design will be conducted with 4 pre-planned interim analyses after 30, 60, and 90 subjects complete the Day 7 evaluation and 150 subjects complete the Day 28 evaluation. At each interim, the DSMB will evaluate an independently conducted analysis in order to assess safety and futility.

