## 6 INTRODUCTION

### 6.1 Background Information

The recently identified severe acute respiratory syndrome coronavirus 2 (SARS-CoV-2) is the cause of the coronavirus disease 2019 (COVID-19) pandemic. SARS-CoV-2 is an enveloped beta coronavirus similar to severe acute respiratory syndrome (SARS) and Middle East respiratory syndrome (MERS), the coronaviruses responsible for the last 2 epidemics in 2003 and 2012, respectively [Li 2020]. Currently, more than 104 million infections have been reported worldwide and continues to overwhelm health care systems. As of 03 Feb 2021, the United States continues to have more cases of coronavirus (>26.5 million, with >450,000 deaths) than any other country and, as is happening globally, there is a resulting critical shortage of hospital beds, intensive care unit (ICU) beds, and equipment, such as personal protective equipment and ventilators. With continuing spikes in coronavirus cases and mutant strains that are more contagious or cause more severe disease, treatments that can prevent progression of disease severity are paramount.

The median incubation time of COVID-19 is approximately 5 days. Symptoms, including fever, dry cough, dyspnea, myalgia, and fatigue, typically develop within 11.5 days [Lauer 2020]. Within a few days of symptom onset, some patients rapidly progress to respiratory failure requiring mechanical ventilation [Zhou 2020]. Elderly patients and those with medical comorbidities (eg, diabetes, hypertension, underlying cardio-pulmonary disease, immunocompromised state, kidney disease, cancer) are at greater risk of developing severe pneumonia, which can progress to acute respiratory distress syndrome requiring prolonged care in the ICU. These patients also have a higher mortality rate compared to younger patients without comorbid conditions [Zhou 2020].

Patients with COVID-19 may progress to respiratory failure requiring mechanical ventilation. The clinical condition can be further complicated by the development of acute cardiac injury (due to myocarditis or demand ischemia or both), as well as acute kidney injury [Perico 2020]. These data suggest that cardio-renal protective treatments are an important aspect of medical care in patients with COVID-19 and may impact prognosis.

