## **9 STUDY POPULATION**

### **9.1 Inclusion Criteria**

Eligible subjects must meet all of the following criteria:

1. Male or female,  $\geq 18$  years of age at Screening.
2. Confirmed infection with SARS-CoV-2.
3. High risk of COVID-19 disease progression, defined as:
  - a. 18-69 years of age with lymphopenia AND at least 1 risk factor (described below)
  - b. 18-69 years of age without lymphopenia AND at least 2 risk factors (described below)
  - c.  $\geq 70$  years of age with lymphopenia OR at least 1 risk factor (described below)

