### **9.3 Study Design**

This is a Phase 2, randomized, placebo-controlled, multicenter study that will evaluate the efficacy, tolerability, and safety of a single dose of RBT-9 on the progression of COVID-19 infection in non-critically ill adults who are at high risk due to age and/or comorbid conditions. Subjects with documented SARS-CoV-2 infection who are at high risk for disease progression, as defined in the inclusion criteria (see [Section 9.1](#)), and require observation and/or treatment in a hospital will be screened for entry into the study. Eligible subjects will be stratified by time since COVID-19 diagnosis (<48 hours,  $\geq$ 48 hours) and randomly assigned in a 2:1 ratio to receive a single intravenous infusion of 90 mg RBT-9 or placebo (normal saline). No more than 24 hours can elapse between Screening and Dosing of RBT-9.

All subjects will be assessed through Day 56. All subjects, regardless of hospitalization status, will be assessed on Days 7, 14, 21, and 28, according to the Event Schedule (see [Section 5.1](#)). Assessments will include severity of COVID-19 measured by the 8-point WHO Ordinal Clinical Scale, physical examination, vital signs, clinical laboratory evaluations, concomitant medications, and adverse events. For subjects who have been discharged from the hospital, visits on Days 7, 14, and 21 will be conducted virtually (eg, by telephone or video contact). The Day 28 visit should be conducted in person, but may be conducted virtually, as well. Subjects will also be assessed at safety follow-up visits, which will be conducted virtually (eg, by telephone or video contact) on Days 42 and 56.

An independent data and safety monitoring board (DSMB) will actively monitor interim data to make recommendations regarding study conduct/continuation. The DSMB will meet once the first 30 subjects complete the Day 7 assessment to perform the first interim analysis of the safety data. Enrollment of 30 additional subjects will proceed if the safety profile of RBT-9 is deemed acceptable (as determined by the DSMB). Two additional DSMB interim analyses will be performed once 60 and 90 subjects complete the Day 7 evaluation. The last DSMB interim analysis will be performed once 150 subjects complete the Day 28 evaluation; sample size re-estimation will also be performed to allow a sample size increase to 252 subjects based on pre-defined conditional power rules.

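### The primary analysis names no deciding test, and neither listed test uses the Screening risk variables, so a modest gain in precision and protection against chance imbalance is forgone

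*Combined protocol and SAP*

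**What the plan says.** Section 11.1 defines the primary endpoint as "Percentage of subjects in each treatment group in categories 4 through 8 of the 8-point WHO Ordinal Clinical Scale through Day 28". Section 11.3 lists a two-sided Fisher exact test, without covariates, and then an analysis "using a logistic regression model to control for the stratification factors; the method of Firth will be used to predict outcomes". Section 11.4 repeats the pair. The synopsis identifies the covariate: "a logistic regression model to control for the stratification factor (time since COVID-19 diagnosis". Sections 11.3 and 11.4 write of factors in the plural, but Section 9.3 gives only one ("Eligible subjects will be stratified by time since COVID-19 diagnosis", split at 48 hours), and Section 9.6 asks sites to enter only that one before randomization.

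Inclusion criterion 3 in Section 9.1 defines high risk of progression through age, lymphopenia and a list of nine risk factors. Its first branch reads "18-69 years of age with lymphopenia AND at least 1 risk factor (described below". One of the nine is "Oxygen saturation between 90 and 95% with or without supplemental oxygen". Section 6.1 adds that "Elderly patients and those with medical comorbidities" are at greater risk of severe pneumonia.

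The Event Schedule and Section 9.7.1 collect the relevant values at Screening: demographics, leukocyte differential, SpO2, FiO2 and the WHO category. None of them enters an efficacy model in the text. Section 11 refers to a separate Statistical Analysis Plan for full detail, and no such separate text is in the document supplied.

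**The concern.** A trial that enrols on prognostic variables and records them before randomization can put them in its analysis at almost no cost. Doing so usually sharpens the treatment comparison. It also keeps a chance difference in patient mix from being read as a drug effect, which matters with only 84 placebo subjects.

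Oxygenation deserves particular attention. Category 4 is hospital care with oxygen by mask or nasal prongs, and it counts as failure. Criterion 3 admits subjects with or without supplemental oxygen, and exclusion 4 bars oxygen users only when saturation is below 90%. Some subjects may therefore be in category 4 at Screening, yet baseline respiratory status is neither stratified nor modelled.

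The choice is also unsettled one level up. With two analyses listed and no rule between them, adding covariates to the logistic model helps only if that model decides.

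**Working it through.** **1. The plan's own power (Section 11.6).** Inputs: 84 placebo and 168 RBT-9 subjects, two-sided alpha 0.045 (z = 2.0047), chi-square test without covariates. For 25% vs 10%:

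- pooled rate = (84 × 0.25 + 168 × 0.10)/252 = 37.8/252 = 0.15
- SE under the null = √[0.15 × 0.85 × (1/84 + 1/168)] = 0.0477
- SE under the alternative = √[0.25 × 0.75/84 + 0.10 × 0.90/168] = 0.0526
- power = Φ[(0.15 − 2.0047 × 0.0477)/0.0526] = Φ(1.03) = 84.9%

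The same formula gives 85.6% for 32% vs 15% and 84.6% for 38% vs 20%. The plan states 84, 85 and 84%, so its power reproduces without any covariate. By exact enumeration the Fisher test has 83.6, 84.0 and 82.5%. That small shortfall comes from the exact test, not from missing covariates.

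**2. Power gained by adjusting.** The documents give no prevalences or odds ratios for these variables, so both are assumed. Trials of 252 subjects (2:1) were simulated, 2,500 per setting, with event rates held at the protocol's three scenarios. A Firth logistic Wald test at 0.045 was fitted with the stratum alone, then with age ≥70, lymphopenia and SpO2 90-95% added. In the last column, criterion 3 was imposed on the simulated population. Before selection, the assumed prevalences there were 30, 45 and 45%; among those eligible they were 37, 54 and 54%.

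| Assumed odds ratio for failure | Change in power, covariates independent (points) | Change in power, criterion 3 imposed (points) |
|---|---|---|
| 1.3 each | −0.3 to +0.1 | −1.0 to −0.1 |
| 2 each | +1.3 to +1.7 | +0.3 to +1.2 |
| 3 each | +2.7 to +3.6 | +1.4 to +2.2 |
| SpO2 6, others 2 | +2.9 to +4.8 | +2.8 to +4.2 |

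Simulation error of each power is √(0.85 × 0.15/2,500) = 0.7 points. The eligibility rule shrinks most gains because a subject lacking one risk marker must have another: pairwise correlations among the three were −0.08 to −0.09. For scale, in the 32% vs 15% scenario +2 points of power equals 270 − 252 = 18 more subjects, and +5 points equals 300 − 252 = 48.

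**3. Chance imbalance.** For a binary covariate with prevalence p, the SE of the between-arm difference is √[p(1 − p)(1/n1 + 1/n2)], and the probability of a gap of at least 10 points in either direction is 2[1 − Φ(0.10/SE)].

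| p | SE, N = 252 | Probability, N = 252 | Probability, N = 150 (50/100) |
|---|---|---|---|
| 0.3 | 0.0612 | 10.2% | 20.8% |
| 0.4 | 0.0655 | 12.7% | 23.9% |
| 0.5 | 0.0668 | 13.4% | 24.8% |

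**4. Type 1 error.** Under the null (32% in both arms, SpO2 odds ratio 6, others 2, criterion 3 imposed, 6,000 trials), two-sided error was 4.3% without and 4.4% with adjustment, against a nominal 4.5%. In the 7.35% of trials (441) where SpO2 mix favoured RBT-9 by 10 points or more, false rejection in favour of RBT-9 was 7.9% without and 3.2% with adjustment (nominal 2.25%). The simulation errors are √(0.079 × 0.921/441) = 1.3 points and √(0.032 × 0.968/441) = 0.8 points.

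**5. Room for covariates.** Expected failures are 84 × 0.25 + 168 × 0.10 = 38 at the low end and 84 × 0.38 + 168 × 0.20 = 66 at the high end. That supports a handful of terms, not a long list. At the 60-subject interim (20/40) the low-end figure is 20 × 0.25 + 40 × 0.10 = 9, even at the Day 28 rates.

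**The case against.** The case for leaving the plan alone is substantial:

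- The Fisher test is listed first, the sample size rests on an unadjusted chi-square test, and the futility rule is worded in terms of percentages in categories 4 to 8. If Fisher decides, covariates in the logistic model change nothing.
- The gain rests wholly on assumed covariate strengths. It is nil or slightly negative when they are weak, and reaches 4 points or more only with a very strong SpO2 effect.
- A raw SpO2 term would mix room-air and oxygen-supported values. The text gives no lymphopenia threshold, and laboratories are local.
- The announced separate plan may yet name covariates.

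All of this stands as a limit on size and wording. It does not remove the point: the present text prespecifies no baseline risk variable and no deciding analysis. In an open-label trial (Sections 9.6 and 10.5), covariates chosen after outcome data accrue would invite criticism.

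A reader might infer four stronger things that the documents do not support:

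- **Planned power is lost.** It is not, since the stated figures never assumed adjustment.
- **The 7.9% in step 4 shows an inflated Type 1 error.** It is conditional on an imbalance seen in about 7% of trials under a strong assumption; the overall rate holds.
- **Age, lymphopenia and SpO2 alone decide eligibility.** SpO2 is one of nine risk factors.
- **Time since diagnosis is the weaker predictor.** No figure supports this, and the early-treatment rationale in Sections 6.1 and 6.2 explains why it was chosen as the stratum.

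**Conclusion.** The point holds as a worthwhile improvement, not as a flaw in validity. Two analyses of the primary endpoint are listed without an order of authority, and neither uses the baseline variables by which the protocol itself marks high risk, or the Screening WHO category.

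Adjusting would change power by between about nil (−1.0 to +0.1 points at odds ratios of 1.3) and 4-5 points (one very strong oxygenation covariate). It would also guard against imbalances that arise in 10-13% of trials per covariate at N = 252, and 21-25% at the 150-subject interim. Such an imbalance matters only for a covariate that is truly prognostic. These sizes rest on assumed prevalences and odds ratios and on no dropout.

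Oxygenation is the most plausible strong candidate, because the failure definition begins at oxygen use. The documents do not say how many subjects will be on oxygen at entry. Nor do they show that such a subject is a failure from the outset, since they do not state whether Screening or Day 1 status counts toward the endpoint.

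**What to change.** In Sections 11.3 and 11.4 and the synopsis:

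- Name the Firth logistic model as the deciding analysis, with treatment, the diagnosis-time stratum and a short prespecified list of Screening covariates: age (continuous), lymphopenia (yes/no, with its threshold stated) and baseline respiratory status. The last can be the Screening WHO category, or SpO2 together with supplemental oxygen use.
- Report the adjusted risk difference beside the odds ratio, and keep the Fisher test as supportive.
- In Sections 9.3.1 and 11.7, state which analysis the conditional-power rules use at each look, given how few failures the early looks will have.
- Settle the list before outcome data by arm are seen.

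No new data are needed. The cost is wording, plus aligning the conditional-power basis and noting in Section 11.6 that the sample size rests on an unadjusted test. The downsides are small: the odds ratio becomes conditional on the covariates, and weak covariates would leave power unchanged or slightly lower. Comorbidity is left off only to keep the model short; the sponsor could reasonably choose otherwise if the list stays short.
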